11.1 Data collection

Designated investigator staff will enter the data required by the protocol into the Electronic Case Report Forms (eCRF). The eCRFs have been built using fully validated secure web-enabled software that conforms to 21 CFR Part 11 requirements. Investigator site staff will not be given access to the EDC system until they have been trained. Automatic validation programs check for data discrepancies in the eCRFs, allow modification and/or verification of the entered data by the investigator staff.

The investigator/designee is responsible for assuring that the data entered into eCRF is complete, accurate, and that entry and updates are performed in a timely manner. The Investigator must certify that the data entered are complete and accurate. After final database lock, the investigator will receive copies of the subject data for archiving at the investigational site. All data should be recorded, handled and stored in a way that allows its accurate reporting, interpretation and verification.

11.2 Database management and quality control

Novartis personnel (or designated CRO) will review the data entered by investigational staff for completeness and accuracy. Electronic data queries stating the nature of the problem and requesting clarification will be created for discrepancies and missing values and sent to the investigational site via the EDC system. Designated investigator site staff are required to respond promptly to queries and to make any necessary changes to the data.

Concomitant treatments and prior medications entered into the database will be coded using the WHO Drug Reference List, which employs the Anatomical Therapeutic Chemical classification system. Medical history/current medical conditions and adverse events will be coded using the Medical dictionary for regulatory activities (MedDRA) terminology.

Laboratory samples will be processed centrally and the results will be sent electronically to Novartis. ECG readings will be processed centrally and the results will be sent electronically to Novartis. Diary data will be entered into an electronic diary by the subject. The system will be supplied by a vendor, who will also manage the database. The database will be sent electronically to Novartis.

Randomization codes and data about all study treatment (s) dispensed to the subject and all dosage changes will be tracked using an Interactive Response Technology (IRT). The system will be supplied by a vendor, who will also manage the database. The data will be sent electronically to Novartis at specific timelines.

[figure not shown]
Each occurrence of a code break via IRT will be reported to the clinical team and monitor. The code break functionality will remain available until study shut down or upon request of Novartis.

Once all the necessary actions have been completed and the database has been declared complete and accurate, it will be locked and made available for data analysis. Any changes to the database after that time can only be made after written agreement by Novartis development management.

11.3 Site monitoring

Before study initiation, at a site initiation visit or at an investigator's meeting, a Novartis representative will review the protocol and data capture requirements with the investigators and their staff. During the study, Novartis employs several methods of ensuring protocol and GCP compliance and the quality/integrity of the sites' data. The field monitor will visit the site to check the completeness of subject records, the accuracy of data capture / data entry, the adherence to the protocol and to Good Clinical Practice, the progress of enrollment, and to ensure that study treatment is being stored, dispensed, and accounted for according to specifications. Key study personnel must be available to assist the field monitor during these visits. Continuous remote monitoring of each site's data may be performed by a centralized Novartis CRA organization. Additionally, a central analytics organization may analyze data & identify risks & trends for site operational parameters, and provide reports to Novartis clinical teams to assist with trial oversight.

The investigator must maintain source documents for each subject in the study, consisting of case and visit notes (hospital or site medical records) containing demographic and medical information, laboratory data, electrocardiograms, and the results of any other tests or

assessments. All information on CRFs must be traceable to these source documents in the subject's file. The investigator must also keep the original informed consent form signed by the subject (a signed copy is given to the subject).

The investigator must give the monitor access to all relevant source documents to confirm their consistency with the data capture and/or data entry. Novartis monitoring standards require full verification for the presence of informed consent, adherence to the inclusion/exclusion criteria, documentation of SAEs, and of data that will be used for all primary variables. Additional checks of the consistency of the source data with the CRFs are performed according to the study-specific monitoring plan. No information in source documents about the identity of the subjects will be disclosed.

12 Data analysis and statistical methods

Any data analysis carried out independently by the investigator should be submitted to Novartis before publication or presentation.

The core phase and extension phase data will be analyzed separately.

12.1 Analysis sets

The Full Analysis Set (FAS) comprises all subjects to whom study treatment has been assigned by randomization. According to the intent to treat principle, subjects will be analyzed according to the treatment and stratum they have been assigned to during the randomization procedure.

The Safety Set includes all subjects who received at least one dose of study treatment. Subjects will be analyzed according to the study treatment received, where treatment received is defined as the randomized/assigned treatment if the patient took at least one dose of that treatment or the first treatment received if the randomized/assigned treatment was never received. Open label extension phase analysis set will include subjects who consented to enter Extension Phase and who have taken at least one dose of erenumab in Extension Phase.

12.2 Subject demographics and other baseline characteristics

Demographic variables and other baseline characteristics including previous migraine treatments will be summarized for FAS. Descriptive statistics (mean, median, standard deviation, minimum, and maximum) will be presented for continuous variables for each treatment group and for all participants (total). The number and percentage of participants in each category will be presented for categorical variables for each treatment group and all participants (total). In addition, all relevant medical history will be summarized following the same strategy.

12.3 Treatments

The Safety set will be used for the analyses below. Categorical data will be summarized as frequencies and percentages. For continuous data, mean, standard deviation, median, 25th and 75th percentiles, minimum, and maximum will be presented.

A data listing and a summary of the investigational drug (erenumab or active comparator) administered will be provided. Unless otherwise specified, patients assigned to 70 mg or 140

mg erenumab dose will be analyzed together under one treatment arm erenumab. The analysis by dose will be detailed in SAP as needed.

Concomitant medications and significant non-drug therapies prior to and after the start of the study treatment will be listed and summarized according to the Anatomical Therapeutic Chemical (ATC) classification system, by treatment group.

A data listing and summary of rescue medications will be provided by treatment group.

12.4 Analysis of the primary endpoint(s)

The primary aim of the study is to evaluate the effect of erenumab vs SoC oral prophylactic medications on the net benefit, a measure of sustained long-term benefit in these two treatment paradigms of migraine prophylactic agents.

12.4.1 Definition of primary endpoint(s)

The primary endpoint of the study is the proportion of subjects achieving net benefit, defined as completion of one year on the initial treatment AND achieving at least a 50% reduction from baseline in monthly migraine days in the last month (month 12).

12.4.2 Statistical model, hypothesis, and method of analysis

The primary analyses will compare the proportion of subjects in FAS who achieve a net benefit (defined in previous section) between erenumab vs SoC oral prophylactic medications.

To be tested is the null hypothesis that net benefit odds ratio = 1, versus the alternative hypothesis: net benefit odds ratio \neq 1.

A Cochran-Mantel-Haenszel (CMH) test stratified by number of previous treatment failures (1 vs. 2) will be used under a 2-sided significance level of 0.05 to evaluate the association between the net benefit rate and the treatment. The p-value of the test, and the estimated odds ratio between erenumab and active comparator, as well as its 95% confidence interval, will also be reported.

The details on primary and supplementary estimand will be provided in estimand charter or statistical analysis plan (SAP).

12.4.3 Handling of missing values/censoring/discontinuations

Subjects with missing monthly migraine day data at month 12 of treatment, and subjects that discontinue initial treatment prior to month 12 will be imputed as non-responders (not achieving a net benefit).

12.4.4 Sensitivity and Supportive analyses

The sensitivity and supportive analysis will be detailed in SAP.

12.5 Analysis of secondary endpoints

12.5.1 Efficacy and/or Pharmacodynamic endpoint(s)

- Proportion of subjects completing the treatment period at month 12 on the initially assigned treatment

This variable will be analyzed same as that of the primary endpoint.

- Global satisfaction as measured by PGI at month 12 for subjects completing treatment period on initially assigned treatment

Patient will be considered as responder if PGI-I score is 5, 6, or 7. Proportion of responders based on PGI-I score at month 12 will be analyzed same as that of the primary endpoint.

- Cumulative average change from baseline on the monthly migraine days during the treatment period for subjects on the initially assigned treatment (month 1-12)

The average of monthly migraine days will be obtained cumulatively at each month across 12 months (e.g. at month 2 the average will be based on data from month 1 and 2; at month 3 the average will be based on month 1 to 3 and so on). The cumulative average change from baseline on the monthly migraine days will be derived using difference between cumulative average at each month and baseline monthly migraine days. The change from baseline will be analyzed using a linear mixed effects model including treatment group, baseline value, stratification factor(s), scheduled visit, and the interaction of treatment group with scheduled visit.

12.5.2 Safety endpoints

For all safety analyses, the safety set will be used. All listings and tables will be presented by treatment group.

Safety summaries (tables, figures) include only data from the on-treatment period with the exception of baseline data which will also be summarized where appropriate (e.g. change from baseline summaries). In addition, a separate summary for death including on treatment and post treatment deaths will be provided. In particular, summary tables for adverse events (AEs) will summarize only on-treatment events, with a start date during the on-treatment period (*treatment-emergent* AEs).

The on-treatment period lasts from the date of first administration of study treatment to 112 days after the date of the last actual administration of any study treatment.

Adverse events

All information obtained on adverse events will be displayed by treatment group and subject.

The number (and percentage) of subjects with treatment-emergent adverse events (events started after the first dose of study medication) will be summarized in the following ways:

- by treatment, primary system organ class and preferred term.
- by treatment, primary system organ class, preferred term and maximum severity.
- by treatment, Standardized MedDRA Query (SMQ) and preferred term

Separate summaries will be provided for study medication related adverse events, death, serious adverse events, other significant adverse events leading to discontinuation and adverse events leading to dose adjustment.

A subject with multiple adverse events within a primary system organ class is only counted once towards the total of the primary system organ class.

Vital signs

All vital signs data will be listed by treatment group, subject, and visit and if ranges are available, abnormalities will be flagged. Summary statistics will be provided by treatment.

12-lead ECG

All ECG data will be listed by treatment group, subject and visit/time, abnormalities will be flagged. Summary statistics will be provided by treatment.

Clinical laboratory evaluations

All laboratory data will be listed by treatment group, subject, and visit and if normal ranges are available abnormalities will be flagged. Summary statistics will be provided by treatment. Shift tables using the low/normal/high/ (low and high) classification will be used to compare baseline to the worst on-treatment value.

[REDACTED]

[REDACTED]

[REDACTED]

[REDACTED]

12.5.3 Pharmacokinetics

Not applicable.

12.5.4 DNA

Not applicable.

12.5.5 Biomarkers

Not applicable.

12.5.6 PK/PD relationships

Not applicable.

[REDACTED]

[REDACTED]

[REDACTED]

[REDACTED]

12.7 Interim analyses

Not Applicable.

12.8 Sample size calculation

12.8.1 Primary endpoint(s)

The sample size calculation is based on the primary variable, rate of net benefit. The details of hypothesis testing are described in [Section 12.4.2](#).

A 2-sided test with significance level 0.05, and a 2:1 randomization ratio are considered. A sample size of 591 (394 erenumab arm; 197 control arm) is required to achieve 90% power to reject the odds ratio of 1 set by the null hypothesis when the odds ratio is actually 2, and success rate in control arm is 0.18.

An odds ratio of 2 and control rate of 0.18 is based on more conservative assumptions for rate of net benefit than observed previously (for erenumab in studies NCT02456740, NCT01952574, and oral prophylactics in [Hepp et al 2017](#), [Shei et al 2015](#)), resulting in a rate difference of 12%. Sample size calculations were done using PASS 11 and Cochran-Mantel-Haenszel test.

13 Ethical considerations and administrative procedures

13.1 Regulatory and ethical compliance

This clinical study was designed and shall be implemented, executed and reported in accordance with the ICH Harmonized Tripartite Guidelines for Good Clinical Practice, with applicable local regulations (including European Directive 2001/20/EC, US CFR 21), and with the ethical principles laid down in the Declaration of Helsinki.

In the US, Amgen will be the sponsor and all responsibilities for the conduct of this clinical study will be transferred to Novartis. In all other countries, Novartis will be the sponsor and maintain all responsibilities for the conduct of the clinical study.

13.2 Responsibilities of the investigator and IRB/IEC

Before initiating a trial, the investigator/institution must obtain approval/favorable opinion from the Institutional Review Board/Independent Ethics Committee (IRB/IEC) for the trial protocol, written informed consent form, consent form updates, subject recruitment procedures (e.g., advertisements) and any other written information to be provided to subjects. Prior to study start, the investigator is required to sign a protocol signature page confirming his/her agreement

[REDACTED]

to conduct the study in accordance with these documents and all of the instructions and procedures found in this protocol and to give access to all relevant data and records to Novartis monitors, auditors, Novartis Quality Assurance representatives, designated agents of Novartis, IRBs/IECs, and regulatory authorities as required. If an inspection of the clinical site is requested by a regulatory authority, the investigator must inform Novartis immediately that this request has been made.

13.3 Publication of study protocol and results

The protocol will be registered in a publicly accessible database such as clinicaltrials.gov and as required in EudraCT. In addition, after study completion (*defined as last patient last visit*) and finalization of the study report the results of this trial will be submitted for publication and posted in a publicly accessible database of clinical trial results, such as the Novartis clinical trial results website and all required Health Authority websites (e.g. Clinicaltrials.gov, EudraCT etc.) .

An initial study report will be prepared and finalized for all data from the Core Phase. A second and study report will be prepared for the Extension Phase after all patients have completed their respective last visit (LPLV) of the Extension Phase.

For details on the Novartis publication policy including authorship criteria, please refer to the Novartis publication policy training materials that were provided to you at the trial investigator meetings.

13.4 Quality Control and Quality Assurance

[figure not shown]
Novartis maintains a robust Quality Management System (QMS) that includes all activities involved in quality assurance and quality control, to ensure compliance with written Standard Operating Procedures as well as applicable global/local GCP regulations and ICH Guidelines.

Audits of investigator sites, vendors, and Novartis systems are performed by auditors, independent from those involved in conducting, monitoring or performing quality control of the clinical trial. The clinical audit process uses a knowledge/risk based approach.

Audits are conducted to assess GCP compliance with global and local regulatory requirements, protocols and internal SOPs, and are performed according to written Novartis processes

14 Protocol adherence

This protocol defines the study objectives, the study procedures and the data to be collected on study participants. Additional assessments required to ensure safety of subjects should be administered as deemed necessary on a case-by-case basis. Under no circumstances including incidental collection is an investigator allowed to collect additional data or conduct any additional procedures for any purpose involving any investigational drugs under the protocol, other than the purpose of the study. If despite this interdiction prohibition, data, information, observation would be incidentally collected, the investigator shall immediately disclose it to Novartis and not use it for any purpose other than the study, except for the appropriate monitoring on study participants.

Investigators ascertain they will apply due diligence to avoid protocol deviations. If an investigator feels a protocol deviation would improve the conduct of the study this must be considered a protocol amendment, and unless such an amendment is agreed upon by Novartis and approved by the IRB/IEC and health authorities, where required, it cannot be implemented.

16.1 Appendix 1: Clinically notable laboratory values and vital signs

Table 16-1 Clinically Notable Laboratory Values

Laboratory Variable	Gender (M/F/Both)	Standard Units	SI Units
LIVER FUNCTION AND RELATED VARIABLES			
SGOT (AST)	F	>93 U/L	>93 U/L
SGOT (AST)	M	>111 U/L	>111 U/L
SGPT (ALT)	F	>90 U/L	>90 U/L
SGPT (ALT)	M	>123 U/L	>123 U/L
Total bilirubin	Both	>3.6 mg/dL	>63 mmol/L
Alkaline Phosphatase	F	>832 U/L	>832 U/L
Alkaline Phosphatase	M	>1032 U/L	>1032 U/L

16.2 Appendix 2: Liver event and Laboratory trigger Definitions and Follow-up Requirements

Table 16-2 Liver Event and Laboratory Trigger Definitions

	Definition/ threshold
LIVER LABORATORY TRIGGERS	
• $3 \times \text{ULN} < \text{ALT} / \text{AST} \leq 5 \times \text{ULN}$• $1.5 \times \text{ULN} < \text{TBL} \leq 2 \times \text{ULN}$
LIVER EVENTS	
• ALT or AST $> 5 \times \text{ULN}$• ALP $> 2 \times \text{ULN}$ (in the absence of known bone pathology)• TBL $> 2 \times \text{ULN}$ (in the absence of known Gilbert syndrome)• ALT or AST $> 3 \times \text{ULN}$ and INR > 1.5• Potential Hy's Law cases (defined as ALT or AST $> 3 \times \text{ULN}$ and TBL $> 2 \times \text{ULN}$ [mainly conjugated fraction] without notable increase in ALP to $> 2 \times \text{ULN}$)• Any clinical event of jaundice (or equivalent term)• ALT or AST $> 3 \times \text{ULN}$ accompanied by (general) malaise, fatigue, abdominal pain, nausea, or vomiting, or rash with eosinophilia• Any adverse event potentially indicative of a liver toxicity*

*These events cover the following: hepatic failure, fibrosis and cirrhosis, and other liver damage-related conditions; the non-infectious hepatitis; the benign, malignant and unspecified liver neoplasms

TBL: total bilirubin; ULN: upper limit of normal

Note: INR (International Normalized Ratio) measurements are not collected as part of routine lab assessments. If a patient has a liver event please consider to collect an INR to aid in assessing severity.

Table 16-3 Follow Up Requirements for Liver Events and Laboratory Triggers

Criteria	Actions required	Follow-up monitoring
Potential Hy's Law case ^a	
 Discontinue the study treatment immediately Hospitalize, if clinically appropriate Establish causality Complete liver CRF 	ALT, AST, TBL, Alb, PT/INR, ALP and γGT until resolution ^c (frequency at investigator discretion)
ALT or AST		
> 8 × ULN	
 Discontinue the study treatment immediately Hospitalize if clinically appropriate Establish causality Complete liver CRF 	ALT, AST, TBL, Alb, PT/INR, ALP and γGT until resolution ^c (frequency at investigator discretion)
> 3 × ULN and INR > 1.5	
 Discontinue the study treatment immediately Hospitalize, if clinically appropriate Establish causality Complete liver CRF 	ALT, AST, TBL, Alb, PT/INR, ALP and γGT until resolution ^c (frequency at investigator discretion)
> 5 to ≤ 8 × ULN	
 Repeat LFT within 48 hours If elevation persists, continue follow-up monitoring If elevation persists for more than 2 weeks, discontinue the study drug Establish causality Complete liver CRF 	ALT, AST, TBL, Alb, PT/INR, ALP and γGT until resolution ^c (frequency at investigator discretion)
> 3 × ULN accompanied by symptoms ^b	
 Discontinue the study treatment immediately Hospitalize if clinically appropriate Establish causality Complete liver CRF 	ALT, AST, TBL, Alb, PT/INR, ALP and γGT until resolution ^c (frequency at investigator discretion)
> 3 to ≤ 5 × ULN (patient is asymptomatic)	
 Repeat LFT within the next week If elevation is confirmed, initiate close observation of the patient 	Investigator discretion Monitor LFT within 1 to 4 weeks
ALP (isolated)		

Criteria	Actions required	Follow-up monitoring
> 2 × ULN (in the absence of known bone pathology)	
 Repeat LFT within 48 hours If elevation persists, establish causality Complete liver CRF 	Investigator discretion Monitor LFT within 1 to 4 weeks or at next visit
TBL (isolated)		
> 2 × ULN (in the absence of known Gilbert syndrome)	
 Repeat LFT within 48 hours If elevation persists, discontinue the study drug immediately Hospitalize if clinically appropriate Establish causality Complete liver CRF 	ALT, AST, TBL, Alb, PT/INR, ALP and γGT until resolution ^c (frequency at investigator discretion) Test for hemolysis (e.g., reticulocytes, haptoglobin, unconjugated [indirect] bilirubin)
> 1.5 to ≤ 2 × ULN (patient is asymptomatic)	
 Repeat LFT within the next week If elevation is confirmed, initiate close observation of the patient 	Investigator discretion Monitor LFT within 1 to 4 weeks or at next visit
Jaundice	
 Discontinue the study treatment immediately Hospitalize the patient Establish causality Complete liver CRF 	ALT, AST, TBL, Alb, PT/INR, ALP and γGT until resolution ^c (frequency at investigator discretion)
Any AE potentially indicative of a liver toxicity*	
 Consider study treatment interruption or discontinuation Hospitalization if clinically appropriate Establish causality Complete liver CRF 	Investigator discretion

^aElevated ALT/AST > 3 × ULN and TBL > 2 × ULN but without notable increase in ALP to > 2 × ULN

^b(General) malaise, fatigue, abdominal pain, nausea, or vomiting, or rash with eosinophilia

^cResolution is defined as an outcome of one of the following: (1) return to baseline values, (2) stable values at three subsequent monitoring visits at least 2 weeks apart, (3) remain at elevated level after a maximum of 6 months, (4) liver transplantation, and (5) death.

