10.2 Additional Safety Monitoring

10.2.1 Liver safety monitoring

To ensure subject safety and enhance reliability in determining the hepatotoxic potential of an investigational drug, a standardized process for identification, monitoring and evaluation of liver events has to be followed.

The following two categories of abnormalities / adverse events have to be considered during the course of the study (irrespective of whether classified/reported as AE/SAE):

- Liver laboratory triggers, which will require repeated assessments of the abnormal laboratory parameter
- Liver events, which will require close observation, follow-up monitoring

Please refer to [Section 16.2](#) for complete definitions of liver laboratory triggers and liver events.

Every liver event defined in [Table 16-2](#) should be followed up by the investigator or designated personnel at the trial site, as summarized below. Additional details on actions required in case of liver events are outlined in [Table 16-3](#). Repeat liver chemistry tests (ALT, AST, TBL, PT/INR, ALP and G-GT) to confirm elevation.

These liver chemistry repeats will be performed using the central laboratory. If results will not be available from the central laboratory, then the repeats can also be performed at a local laboratory to monitor the safety of the subject. If a liver event is subsequently reported, any local liver chemistry tests previously conducted that are associated with this event should have results reported on the unplanned local laboratory CRF.

- If the initial elevation is confirmed, close observation of the subject will be initiated, including consideration of treatment interruption if deemed appropriate.
- Discontinuation of the investigational drug (refer to the Discontinuation of study treatment section), if appropriate
- Hospitalization of the subject if appropriate
- Causality assessment of the liver event
- Thorough investigation of the liver event -
 - These investigations can include based on investigator's discretion: serology tests, imaging and pathology assessments, hepatologist's consultancy; obtaining more

detailed history of symptoms and prior or concurrent diseases, history of concomitant drug use, exclusion of underlying liver disease

All follow-up information, and the procedures performed must be recorded as appropriate.

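### For an asymptomatic, isolated ALT/AST above 3 and up to 5 × ULN, the protocol is ambiguous about whether INR must be measured, so a mandatory stop criterion can go untested

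*Protocol*

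**What the plan says.** Protocol Section 16.2 defines two tiers. Table 16-2 classes ALT or AST above 3 and up to 5 × ULN as a laboratory trigger. It classes ALT or AST above 3 × ULN together with INR above 1.5 as a liver event. In Table 16-3 the row "> 3 × ULN and INR > 1.5" carries an immediate stop of study treatment.

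On when INR is measured, the text says:

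- Note to Table 16-2: INR "measurements are not collected as part of routine lab assessments". It continues: "If a patient has a liver event please consider to collect an INR to aid in assessing severity".
- Section 10.2.1, on triggers: "Liver laboratory triggers, which will require repeated assessments of the abnormal laboratory parameter".
- Table 16-3, row for asymptomatic ALT/AST above 3 and up to 5 × ULN: "Repeat LFT within the next week", then "If elevation is confirmed, initiate close observation of the patient". The follow-up column leaves the schedule to the investigator and adds "Monitor LFT within 1 to 4 weeks".
- Table 16-3, the other ALT/AST rows: follow-up is "ALT, AST, TBL, Alb, PT/INR, ALP and γGT until resolution".
- Section 10.2.1, in the paragraph that opens with the follow-up of every liver event: a repeat panel of liver tests that includes PT/INR, to confirm the elevation.

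The abbreviation list expands LFT but does not list its component tests.

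**The concern.** In this band, INR decides the category. At 4 × ULN without symptoms, an INR of 1.5 or less leaves the subject a trigger under observation. An INR above 1.5 makes the same subject a liver event with an immediate stop. The note prompts INR only after a liver event has been declared, so for this subject the prompt depends on the result it should produce.

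If the text leaves INR optional here, a site can follow it, confirm the elevation, continue dosing under observation, and never learn whether the stop criterion was met. Section 4.5 states that no data monitoring committee was thought necessary and relies on close clinical monitoring, among other measures. The site-level liver rules therefore carry weight.

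**Working it through.** No arithmetic applies, so the check sets the texts side by side for an illustrative subject: ALT 4 × ULN, no symptoms, normal bilirubin and ALP, INR not yet drawn.

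| Text | Whom it addresses | Does it require INR for this subject? |
|---|---|---|
| Table 16-2, trigger range | ALT/AST above 3 and up to 5 × ULN | Sets the class (trigger); no test named |
| Note to Table 16-2 | Subjects with a liver event | No; not yet a liver event, and the wording is only to consider INR |
| 10.2.1, trigger sentence | Laboratory triggers | No; the abnormal parameter is ALT |
| Table 16-3, row for this subject | Asymptomatic ALT/AST above 3 and up to 5 × ULN | Not named; LFT only, and LFT is not itemised |
| 10.2.1, repeat panel | Placed under the liver-event sentence | Yes if read as covering triggers; no if read by its placement |
| Table 16-3, INR row | ALT/AST above 3 × ULN with INR above 1.5 | Assumes that INR is known |

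Two readings follow.

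1. *Narrow.* The panel belongs to liver events and the trigger sentence governs triggers. The site repeats ALT, confirms 4 × ULN, observes, and monitors LFT. INR is never called for, and the immediate-stop row is not tested.
2. *Broad.* The panel covers any elevation that needs confirming. The site draws PT/INR with the repeat test, and the row can be applied.

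Nothing in the protocol settles which reading is meant. On the narrow one the site has not deviated.

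The limits of the gap can be traced in the same way. Above 5 × ULN, or above 3 × ULN with symptoms, the subject has a liver event; the 10.2.1 panel applies and the Table 16-3 follow-up column names PT/INR. There the only conflict is with the softer wording of the note. Potential Hy's Law values and jaundice lead to an immediate stop under their own rows. What remains is the asymptomatic subject in this band who meets no other stop row and has INR above 1.5.

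On frequency, Table 8-1 (footnote 3) makes chemistry mandatory for the oral arm at four visits: Screening, Treatment, Week 24 and Week 52. Other draws in that arm are as needed. The erenumab row also shows four draws. With the last Core Phase erenumab dose at Week 48, about one scheduled draw (Week 24) falls between the first and last doses. The documents give no rate of ALT/AST elevation in this band and none of INR above 1.5 within it, so no count can be derived.

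**The case against.** The best case for the protocol is that Section 10.2.1 already supplies the INR. After the panel it says that a confirmed initial elevation leads to close observation. In Table 16-3 that sequence, confirm and then observe closely, appears only in the two trigger rows (ALT/AST above 3 and up to 5 × ULN, and bilirubin above 1.5 and up to 2 × ULN). No liver-event row uses it. Section 10.2.1 also speaks of a liver event reported after earlier local tests, which suggests that repeats can come before an event. This is a serious argument, and it is why the point is ambiguity and not omission. It does not settle the matter: the paragraph opens with liver events, the same section says that liver events require close observation, and triggers have their own narrower sentence.

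Three stronger readings are tempting and should not be drawn.

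- *The protocol does not require INR in this band, so the criterion will not be evaluated.* The broad reading is available, and an investigator may order INR on judgement.
- *The band is the only one of five ALT/AST rows without PT/INR, which proves the gap.* The isolated ALP row also names only LFT, yet ALP above 2 × ULN is a liver event to which the 10.2.1 panel applies. A row's silence does not show that INR is not required.
- *The one-to-four-week monitoring interval measures the risk.* On the narrow reading that later draw need not include INR either, so the interval bounds neither exposure nor time to detection.

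It can also be said that Amendment 02 added the note on purpose, and that grading INR by severity is reasonable for an approved drug for which Section 4.5 reports no important identified risk. Section 9.1.1 also obliges the investigator to stop treatment that would harm the subject. These arguments lower the stakes. They do not explain a mandatory stop rule whose input may be left unmeasured.

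**Conclusion.** The point stands as an ambiguity in the safety rules. For an asymptomatic, isolated ALT/AST above 3 and up to 5 × ULN, the protocol does not make clear whether INR must be drawn, and a compliant site can continue dosing without testing a mandatory stop criterion. It should be corrected because the remedy is cheap and the rule concerns stopping treatment.

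The size is small: few subjects, in a number that the documents do not allow to be derived. No effect on the primary endpoint is expected. The conclusion rests on the protocol text alone. Section 8.4.1 refers to a laboratory manual for collection details; if that manual adds INR to repeat draws for triggers, practice may already be right and only the protocol wording needs to follow.

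**What to change.** Three wording changes, made together so that the texts agree:

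1. **Section 10.2.1.** State that the repeat panel (ALT, AST, TBL, PT/INR, ALP, G-GT) applies to liver events and to ALT/AST laboratory triggers, and amend the trigger sentence, which now asks only for the abnormal parameter, to match.
2. **Table 16-3, asymptomatic row above 3 and up to 5 × ULN.** Write: *Repeat LFT and INR within the next week.*
3. **Note to Table 16-2.** Replace the request to consider INR with: *Collect an INR with the first repeat test for any liver event and for any ALT or AST > 3 × ULN.* Tell sites to interpret INR in light of anticoagulant use. Keeping liver events in this sentence preserves the prompt for events without raised ALT/AST, such as isolated ALP.

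The cost is one INR on a repeat draw already required, at the central laboratory or at the local one that 10.2.1 allows. There is one small side effect. The exclusion criteria do not name anticoagulants and no baseline INR is taken, so a raised INR unrelated to liver injury could occasionally lead to a stop. Under Section 12.4.3 that subject would count as a non-responder. This should be rare, and the instruction on interpretation limits it. No analysis changes.
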